5.12 Clinical Criteria for Early Trial Termination

Early trial termination will be the result of the criteria specified below:

1. Incidence or severity of adverse drug reaction in this or other studies indicates a potential health hazard to subjects
2. Plans to modify or discontinue the development of the study drug

In the event of Merck decision to no longer supply study drug, ample notification will be provided so that appropriate adjustments to subject treatment can be made.

6.0 DATA COLLECTION AND EVALUATION

6.1 Data Collection

Data will be prospectively collected and entered into a clinical trials database. The protocol specific data will be entered into Redcap, the electronic case report form. All data will be kept secure. Personal identifiers will not be used when collecting and storing data. An enrollment log will be maintained in the regulatory binder/file which is the only location of personal identifiers with unique subject identification number. The Investigator or physician designee is responsible for providing source documentation and assigning attribution for all AEs.

When patients enter the long-term follow-up period, the following data will be collected:

- Adverse events related to Pembrolizumab
- Survival status which will be collected by phone or clinic visit
- Additional cancer therapy received

6.1.1 Record Keeping

Complete records must be maintained on each patient; these records will consist of the hospital chart as well as any other outside information obtained from outside laboratories, radiology reports, or physician's records. These records will serve as the primary source material that forms the basis for the research record. All relevant data will also be entered on a computer database from which formal analyses are done. The primary source documentation will include patient eligibility data, patient history, flow sheets (including specialty forms for pathology, radiology, or surgery), an off-study summary sheet, and a final assessment by the treating physician.

6.1.2 Forwarding of Patient Data from Other Institutions

Either due to extenuating medical circumstances or for convenience, some patients may elect to have certain routine laboratory studies or protein marker analyses performed at an outside institution between scheduled interval visits to MD Anderson Cancer Center for this protocol. These results will be forwarded to the study designated data manager who will enter the data into the study database. Additional blood or tissue samples drawn on patients enrolled in this protocol between scheduled visits may be forwarded and entered into the database as well.

6.2 Response Criteria

Response assessments will be performed on Day 1 of each cycle during Cycle 1-24 and at the end of Cycle 24.

6.2.1 Light chain only disease

- a) If patient does not have presence of "measurable" serum or urine M-protein (those are negative in electrophoresis), but has either a serum kappa or lambda FREE light chain of 10 mg/dL along with an abnormal kappa to lambda free light chain ratio, patient is considered to have "measurable" disease.
- b) The serum free light chain (FLC) assay is of particular use in monitoring response to therapy in patients who have oligo-secretory disease. When using this assay, it is important to note that the FLC levels vary considerably with changes in renal function and do not solely represent monoclonal elevations. Thus both the level of the involved and the uninvolved FLC isotype (i.e., the involved/uninvolved ratio or involved-uninvolved difference) should be considered in assessing response. The serum FLC assay should be used in assessing response only if the baseline serum and/or urine M proteins are not "measurable" by traditional criteria, and the baseline level of the involved FLC is 10mg/dL and clonal (abnormal ratio). Patients included on the study on the basis of FLC alone (i.e., no measurable serum/urine) should be the only ones who are evaluated using FLC response criteria. The others should follow usual criteria and ignore FLC results.
- c) In order to be classified as a hematologic response, confirmation of serum monoclonal protein, serum immunoglobulin free light chain (when primary determinant of response) and urine monoclonal protein (when primary determinant of

response) results must be made by verification on two consecutive determinations.

- d) Caution must be exercised to avoid rating progression or relapse on the basis of variation of radiological technique alone. Compression fracture does not exclude continued response and may not indicate progression. When progression is based on skeletal disease alone, it should be discussed with the PI before removing the patient from the study.

6.2.2 Evaluation of response Criteria by modified International Myeloma Working Group Criteria for Multiple Myeloma

a) Stringent Complete Response (sCR)

- Complete Response as defined below plus: Normal FLC ratio and absence of clonal cells in bone marrow by immunohistochemistry or immunofluorescence (presence/ absence of clonal cells is based on the kappa/ lambda ratio).

b) Complete Response (CR)

- Negative immunofixation on the serum and urine and disappearance of any soft tissue plasmacytomas and $\leq 5\%$ plasma cells in bone marrow

c) Very Good Partial Response (VGPR)

- Serum and urine M-protein detectable by immunofixation but not on electrophoresis or 90% or greater reduction in serum M-protein plus urine M-protein level $< 100\text{mg}$ per 24h. If the serum and urine M-protein are unmeasurable, a $\geq 90\%$ decrease in the difference between involved and uninvolved FLC levels is required in place of the M-protein criteria.

d) Partial Response (PR)

- $\geq 50\%$ reduction in M protein and reduction in 24-h urinary M-protein by $\geq 90\%$ or to $< 200\text{ mg}$ per 24h. If the serum and urine M-protein are unmeasurable, a $\geq 50\%$ difference between involved and uninvolved FLC levels is required in place of the M-protein criteria

e) Minor Response (MR)

- $\geq 25\%$ but $\leq 49\%$ reduction of serum M protein and reduction in 24-hour urine M-protein by 50%-89%. In addition to this, if present at baseline, 25%-49% reduction in the size of soft tissue plasmacytomas is also required. No increase in size or number of lytic bone lesions (development of compression fracture does not exclude response)

f) Stable Disease (SD)

- Not meeting criteria for CR, VGPR, PR, MR or progressive disease. All categories also require no known evidence of progressive or new bone lesions if radiographic studies were performed. Radiographic studies are not required to satisfy these response requirements.

g) Progressive disease (PD)

- Requires any one or more of the following:
 - Increase of $\geq 25\%$ of best response and/or lowest measurable value in:
 - Serum M-component and/or (absolute increase must be $\geq 0.5\text{ g/dl}$.
The serum M-component increases of $\geq 1\text{ gm/dl}$ are sufficient to define

relapse if starting M-component is ≥ 5 gm/dl.

- Urine M-component and/or (the absolute increase must be ≥ 200 mg/24h
- Only in patients without measureable serum and urine M-protein levels: the difference between involved and uninvolved FLC levels. The absolute increase must be >10 mg/dl.
- Bone marrow plasma cell percentage: the absolute % must be $\geq 10\%$
- Definite development of new bone lesions or soft tissue plasmacytomas or definite increase in size of existing bone lesions or soft tissue plasmacytomas
- Development of that can be attributed solely to the plasma cell proliferative disorder

h) Relapse from CR:

- Any one or more of the following:
 - Reappearance of serum or urine M-protein by immunofixation or electrophoresis
 - Development of $\geq 5\%$ plasma cells in the bone marrow
 - Appearance of any other sign of progression (ie, new plasmacytoma, lytic bone lesion, hypercalcemia)

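### Complete response has no free-light-chain condition for patients assessed only on light chains, and its 5% marrow limit also counts as relapse from CR

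*Combined protocol and SAP*

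**What the plan says.** **Who is assessed on FLC.** Section 6.2.1(a) treats a patient with negative serum and urine electrophoresis as measurable if the involved FLC is 10 mg/dL and the ratio is abnormal. On the use of FLC response criteria, 6.2.1(b) states: "Patients included on the study on the basis of FLC alone (i.e., no measurable serum/urine) should be the only ones" to be evaluated that way.

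**The response categories in 6.2.2.**

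- sCR: "Complete Response as defined below plus: Normal FLC ratio and absence of clonal cells in bone marrow".
- CR: "Negative immunofixation on the serum and urine and disappearance of any soft tissue plasmacytomas", with marrow plasma cells of at most 5%. Nothing on FLC follows.
- VGPR, when M-protein is unmeasurable: at least a 90% "decrease in the difference between involved and uninvolved FLC levels is required in place of the M-protein criteria".
- PR, in the same situation: at least a 50% "difference between involved and uninvolved FLC levels is required in place of the M-protein criteria". The word for a fall is missing here.
- Relapse from CR, under 6.2.2(h), includes: "Development of $\geq 5\%$ plasma cells in the bone marrow".

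**Where the categories are used.** ORR is PR, VGPR, CR and sCR together (6.2.6), and ORR after 8 cycles is the primary endpoint (3.1, 9.0). Under 6.2.3, duration of response runs from the first time response criteria are met to the first documented recurrence or progression.

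**The concern.** Response categories should be nested: whoever meets CR should also meet VGPR and PR. For FLC-only patients they are not. VGPR and PR replace M-protein by an FLC measure, while CR keeps immunofixation, which may already be negative at entry and so carries no information on response. That leaves the marrow as the only part of CR that has to change.

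The primary analysis has little slack. Section 9.0 stops at 0 of 12 responses and rejects the regimen at 2 or fewer of 16, so one misclassified patient can matter at either look.

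The marrow limits raise a smaller question. CR includes 5% and relapse from CR starts at 5%, so one value lies on both sides of a boundary that ends the response.

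**Working it through.** **1. The plan's own design figures.** Inputs from section 9.0: 12 then 16 patients, stop at 0 of 12, reject at 2 or fewer of 16, response rates 5% and 25%.

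- Early stop: 0.95^12 = 0.540 and 0.75^12 = 0.032. The plan says 54% and 3.2%.
- Expected size: 12 + 4 × (1 − 0.540) = 13.84 and 12 + 4 × (1 − 0.032) = 15.87. The plan says 13.8 and 15.9.
- Exact probability of acceptance: 0.0427 at 5% and 0.801 at 25%, within the stated 0.05 and 0.80.

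The design reproduces. The point concerns what is counted as a response.

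**2. Can such a patient enter?** Section 5.1 asks for marrow of at least 10% and/or a serum spike and/or urine protein, so a patient with neither protein must enter on marrow. Marrow of at least 10% with an FLC ratio below 0.125 or above 8 gives two of the three Mayo factors in 5.1.1, without an M-spike. So yes.

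**3. The rules applied as written.** Illustrative patient: immunofixation negative in serum and urine, no plasmacytoma, involved FLC 40 and uninvolved 1 mg/dL before and after (ratio 40, below the exclusion limit of 100), marrow from 20% to 5%. FLC difference: 40 − 1 = 39 both times, a fall of 0%.

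| Category | FLC requirement | Met? |
|---|---|---|
| CR | none | yes |
| VGPR | fall ≥ 90% | no |
| PR, read as a decrease | fall ≥ 50% | no |

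The patient is an ORR responder through CR alone. A hidden FLC condition in CR cannot be presumed, because sCR adds a normal ratio on top of CR.

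**4. Size.** One patient is 1/16 = 6.25 percentage points. The next figures are conditional: they assume that the miscall has happened and that all other patients respond at a true 5%.

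- One false CR in stage 1: stage 1 cannot stop, and acceptance needs at least 2 responses among the other 15. 1 − 0.95^15 − 15 × 0.05 × 0.95^14 = 0.171, against 0.043 by design.
- One false CR in stage 2: 0.167.
- Two in stage 1: at least 1 among the other 14, 1 − 0.95^14 = 0.512.

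Unconditionally, let a share f of patients be FLC-only and a share q of their non-responses be called CR. The apparent response rate is then 0.05 + 0.95 × f × q. Neither f nor q is in the documents.

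| f | q | Apparent rate | Acceptance probability |
|---|---|---|---|
| 5% | 10% | 0.0548 | 0.0535 |
| 5% | 50% | 0.0738 | 0.1086 |
| 10% | 10% | 0.0595 | 0.0655 |
| 10% | 50% | 0.0975 | 0.1991 |

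**5. Marrow limits.** Values of 4% and 4.9% meet CR only, 5.1% and 6% meet the relapse limit only, and 5.0% meets both. The overlap is that single value.

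**The case against.** **Section 6.2.1 already points to FLC.** Paragraph (b) asks that both involved and uninvolved FLC be weighed when judging response. Paragraph (c) requires two consecutive determinations of FLC where it is the main determinant. A careful assessor would hesitate to call CR with FLC unchanged. This stands as mitigation, but neither paragraph gives a threshold for CR.

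**PR fails only on a corrected reading.** Taken literally, a 50% difference between involved and uninvolved FLC is met by any patient with high involved FLC, changed or not. On that reading the patient already counts in ORR through PR, and the CR gap adds no responder. This is right. It means that both wordings can admit a patient whose FLC has not moved; correcting PR alone would leave the CR route open.

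**The exposed group is narrow.** Negative electrophoresis is not enough: immunofixation must be negative in serum and urine. The marrow must fall from at least 10% to at most 5% while FLC does not fall enough for PR. A reader might infer that FLC-only patients are in CR at entry. They are not, because they enter with marrow of at least 10%.

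**Zero response duration.** A reader might infer from the 5% overlap that one marrow sample both establishes and ends the response. Duration starts at the initial response, and M-protein is assessed every cycle while marrow is scheduled after cycles 8 and 24 and at progression, so a PR will usually come first. The relapse wording also speaks of development, which fits a fall to 5% poorly. Zero duration needs CR to be the first response and the same sample to serve for both. What stands is the later marrow: a patient in CR who goes from 3% to 5% meets both limits.

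**Conclusion.** Both inconsistencies are in the text, and both are minor. The CR rule can count an FLC-only patient as a responder with an unchanged FLC difference, at 6.25 points of ORR each. This takes a patient with the specific profile above, and ORR changes only if PR is read as requiring a decrease. How many such patients will enroll is unknown; 0 to 2 of 16 is an assumption, and it includes none. The acceptance probabilities show how sensitive a 3-of-16 boundary is to one patient. They do not predict what will happen.

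The marrow overlap leaves the end of response ambiguous at exactly 5%. It bears on duration of response, a secondary objective, and not on ORR.

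Two further inferences are not supported. The sample size calculation is not in error. Nor do the documents show that a normal FLC ratio is the missing CR condition: they list it under sCR, and the VGPR and PR rules use the FLC difference.

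**What to change.** - In 6.2.2(b), state an FLC condition for CR in patients assessed on FLC, at least as strict as the VGPR condition, so that CR implies VGPR and PR. Whether it uses the difference or the ratio is for the sponsor to decide and state, in line with 6.2.1(b) and 6.2.2(c)–(d).
- In 6.2.2(d), say that the 50% FLC criterion is a decrease. In the same edit, state how minor response is judged in these patients, since 6.2.2(e) has no FLC alternative either.
- Make the marrow limits in 6.2.2(b) and 6.2.2(h) mutually exclusive, by moving the 5% value out of one of them.

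The changes should be made before responses are adjudicated, since the trial is open-label with a single arm. FLC is already measured on Day 1 of each cycle (5.6.1.2), so no test, visit or patient is added and the 12/16 design stands. sCR remains distinct through its requirement of no clonal marrow cells. The only downside is a slightly stricter CR.

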2.0 TRIAL DESIGN

2.1 Trial Design

This will be an open label, single center, single arm, pilot trial based on the established dose from the phase 1 trial.

[figure not shown]
Pembrolizumab 200 mg will be administered as a single agent intravenous infusion every 3 weeks (one cycle=21 days) for up to 24 cycles.

Disease evaluation will be done at baseline and at each cycle. Patients will continue with therapy until they have progressive disease or intolerable side effects for 8 cycles initially, with an option to continue therapy beyond 8 cycles if there is continued clinical benefit without serious adverse events.

In patients who show a continued response (\geq minor response) after 8 cycles, treatment can be continued for an additional 16 cycles to a maximum of 24 cycles.

In patients who show a continued response (\geq minor response) after 8 cycles, but who choose to stop treatment after 8 cycles of therapy and then experience progressive disease within 6 months of treatment stop, treatment can be restarted for an additional 16 cycles to a maximum of 24 cycles.

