5.0 METHODOLOGY

5.1 Entry Criteria

Adult patients (age ≥ 18 years old) with intermediate or high-risk SMM are eligible. Patients need to have clonal bone marrow plasma cells $\geq 10\%$ and/or monoclonal spike in blood of ≥ 3 g/dL and/or monoclonal urine component (Bence jones proteinuria) ≥ 500 mg/24 hours and need to meet subject inclusion criteria and exclusion criteria as per below.

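### Section 6.2.2 is wrong as written in two response rules, with small expected effect: the PR light-chain rule omits the decrease, and the MR urine condition applies without exception

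*Combined protocol and SAP*

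**What the plan says.** **PR, 6.2.2(d).** Serum M-protein must fall by at least half, and urine M-protein must fall by at least 90% or to under 200 mg in 24 hours. If neither is measurable, "a $\geq 50\%$ difference between involved and uninvolved FLC levels is required in place of the M-protein criteria".

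**VGPR, 6.2.2(c).** The parallel substitute is a 90% or greater "decrease in the difference between involved and uninvolved FLC levels is required in place of the M-protein criteria".

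**MR, 6.2.2(e).** The rule is a 25-49% "reduction of serum M protein and reduction in 24-hour urine M-protein by 50%-89" percent. It gives no absolute urine level as an alternative and no condition on baseline urine M-protein. The plasmacytoma requirement in the same bullet applies only to patients who had plasmacytomas at baseline.

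**Stable disease, 6.2.2(f).** This takes everyone who meets neither a response category nor progression.

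**Entry, 5.1.** Urine is one of three alternative routes: marrow plasma cells, serum spike, "and/or monoclonal urine component (Bence jones proteinuria) ≥ 500 mg/24 hours". The Mayo, PETHEMA and SWOG criteria in 5.1.1 do not use urine M-protein.

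**Where the categories are used.** PR or better after 8 cycles is the primary endpoint (3.1, 9.0). MR or better is the clinical benefit rate (3.2, objective 4; 6.2.7). Section 2.1 also uses MR for treatment. With at least MR "after 8 cycles, treatment can be continued for an additional 16 cycles to a maximum of 24 cycles", and a patient with at least MR who stops at cycle 8 and progresses within 6 months qualifies for restart: "treatment can be restarted for an additional 16 cycles to a maximum of 24 cycles". Section 2.1 separately allows treatment past cycle 8, "with an option to continue therapy beyond 8 cycles if there is continued clinical benefit without serious adverse events".

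**The concern.** The PR substitute, taken at its word, tests how unbalanced the two light chains are at one time, not whether the imbalance has shrunk. Imbalance is a feature of the disease at entry, so an FLC-only patient with no change would be scored a responder on the primary endpoint. With acceptance at 3 of 16, one false responder matters.

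The MR rule errs the other way. A patient with no urine M-protein cannot show a 50-89% fall in it. Read strictly, a serum-only patient passes from stable disease straight to PR as the serum fall reaches 50%. At stake are the clinical benefit rate and access to restart.

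**Working it through.** **1. The plan's own design figures (9.0).** Inputs: 12 patients in stage 1, stop at 0 responses; 16 in total, accept at 3 or more; response rates p of 5% and 25%.
- Early stopping: 0.95^12 = 0.540 and 0.75^12 = 0.0317. The plan gives 54% and 3.2%.
- Expected size: 12 + 4 × (1 − 0.540) = 13.84 and 12 + 4 × (1 − 0.0317) = 15.87. The plan gives 13.8 and 15.9.
- Acceptance: the sum over x = 1 to 12 of P(X1 = x) × P(X2 ≥ 3 − x), with X1 ~ Bin(12, p) and X2 ~ Bin(4, p), is 0.0427 at 5% and 0.801 at 25%.

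The design reproduces, and nothing below changes it.

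**2. PR substitute, read literally.** The text does not say of what quantity the 50% is taken. With r the ratio of involved to uninvolved chain:
- As a share of the involved chain: 1 − 1/r, which reaches 50% at r = 2.
- As a share of the uninvolved chain: r − 1, which reaches 50% at r = 1.5.

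The Mayo risk factor in 5.1.1 is a ratio above 8 (or below 0.125, its mirror image). At r = 8 the first measure is 1 − 1/8 = 87.5% and the second is 700%. Assumed example: involved 20 and uninvolved 2 mg/dL, unchanged on treatment. The difference is 18, which is 18/20 = 90% or 18/2 = 900%. The patient passes on either base. Under the VGPR form of words the change is zero and the patient does not respond.

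**3. Worst case for the primary decision.** Assume one FLC-only non-responder is scored PR automatically and the other 15 patients respond at 5%.
- If enrolled in stage 1, the trial always continues and needs 2 more responses: P(Bin(15, 0.05) ≥ 2) = 1 − 0.4633 − 0.3658 = 0.171.
- If enrolled in stage 2: P(X1 ≥ 1 and X1 + X2 ≥ 2), with X1 ~ Bin(12, 0.05) and X2 ~ Bin(3, 0.05), = 0.167.
- With no such patient: 0.0427.

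**4. MR, read strictly (assumed values).**

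| Patient | Serum change | Urine M-protein | Category |
|---|---|---|---|
| Serum-only | 3.0 to 1.8 g/dL (−40%) | none | Stable disease |
| Serum-only | 3.0 to 1.5 g/dL (−50%) | none, so under 200 mg | PR |
| Serum and urine | −40% | 1000 to 300 mg (−70%) | MR |

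The first and third patients have the same serum fall and differ only in whether there was urine protein to reduce.

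**5. Effect on the clinical benefit rate.** Each reclassified patient costs 1/16 = 6.25 points. With assumed counts and Clopper-Pearson 95% intervals:
- 4/16 = 25.0% (7.3 to 52.4)
- one reclassified: 3/16 = 18.8% (4.0 to 45.6)
- two reclassified: 2/16 = 12.5% (1.6 to 38.3)

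The documents do not say how many patients will be serum-only or FLC-only. With none affected, every shift is zero.

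**The case against.** **On PR.** The intent is plain. The VGPR line sits directly above, 3.1 ties the endpoint to the IMWG criteria, and 6.2.1(b) presents the FLC assay as a tool for following response to therapy. Few assessors would call an unchanged patient a responder. Words may also simply have been lost: the progression list in 6.2.2(g) contains "Development of that can be attributed solely to the plasma cell proliferative disorder", with its subject missing, while the matching item in 5.11 names hypercalcemia. This stands. It makes the PR line a wording slip, to be checked against the signed protocol before amending. It does not make the line correct.

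**On MR.** A reader might infer that MR simply cannot be reached without urine M-protein. That depends on a strict reading. Read equally strictly, the PR urine clause also asks for a reduction, and a sensible assessor would treat both as met when there is nothing to reduce. This too stands in part. The rules still differ: PR offers an absolute level that a serum-only patient already satisfies, whereas MR offers only a percentage fall. The drafters wrote a baseline condition for plasmacytomas in the same bullet and none for urine. The phrase in 6.2.1(c) about urine as the primary determinant of response governs repeat confirmation and waives nothing.

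**On reach.** The clinical benefit rate is secondary, and 9.0 gives it no hypothesis or threshold. Continuation has the separate clinical-benefit route in 2.1. Loss of restart needs a serum-only patient with a 25-49% fall who stops at cycle 8, progresses within 6 months, again meets the entry criteria apart from the prior-treatment exclusions, and is scored strictly. All of this stands and limits the size.

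**On MR for FLC-only patients.** A reader might infer that the plan must also give them an MR rule. VGPR and PR each have an FLC substitute, MR has none, and 6.2.1(b) directs these patients to FLC criteria. The natural reading is that they have no MR category; adding one would be a design preference.

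**Conclusion.** Both rules are wrong as written and worth correcting, but the expected effect is small. The PR wording touches the primary endpoint only if an FLC-only patient enrols and is scored by the literal text. The MR wording costs 6.25 points of clinical benefit rate per affected patient at n = 16, and closes the MR-based restart route, only if the urine clause is applied strictly to serum-only patients.

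A reader might infer that the trial's false-acceptance rate is 17%, or that the primary decision is unsound. The documents do not support either. The 17% is a worst case for one FLC-only non-responder scored by a rule that was evidently not meant. Under the evident intent the rate stays at 4.3%, and MR plays no part in the stop-at-0/12 or reject-at-2/16 decisions.

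**What to change.** - **PR, 6.2.2(d):** for patients with unmeasurable serum and urine M-protein, require a decrease from baseline of at least 50% in the involved-minus-uninvolved FLC difference, in line with the VGPR rule. Check the line against the signed protocol first.
- **MR, 6.2.2(e):** apply the 50-89% urine reduction only when urine M-protein is measurable at baseline, as the bullet already does for plasmacytomas.

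The cost is two wording edits. Sample size, cut-offs, eligibility, visits and tests do not change.

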3.2 Secondary Objectives & Hypotheses

(1) **Objective:** TTP (time to progression to multiple myeloma) at 30 months from study entry

(2) **Objective:** Duration of response

(3) **Objective:** Safety and tolerability

(4) **Objective:** Clinical benefit rate (minor response [MR] or better) after 8 cycles of treatment per modified IMWG criteria for MM

(5) **Objective:** Overall survival

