6.2.7 Clinical Benefit Rate after 8 and 24 cycles of treatment

Clinical benefit rate (CBR) is sCR+CR+VGPR+PR+MR.

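### Minor response is capped in both serum and urine, so a patient who exceeds one band without reaching PR is scored stable disease and drops out of the clinical benefit rate

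*Combined protocol and SAP*

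**What the plan says.** Section 6.2.2 of the protocol sets the response categories.

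- **MR (e):** a serum M-protein fall of at least 25% and at most 49%, joined by *and* to a 24-hour urine fall that is also bounded on both sides: "reduction of serum M protein and reduction in 24-hour urine M-protein by 50%-89" percent. A soft-tissue plasmacytoma present at baseline must also shrink by 25-49%.
- **PR (d):** a serum fall of at least 50%, joined to a urine condition ("reduction in M protein and reduction in 24-h urinary M-protein by" at least 90%, or to under 200 mg/24h). A free light chain (FLC) substitute is given when serum and urine are unmeasurable.
- **VGPR (c), reduction limb:** "90% or greater reduction in serum M-protein plus urine M-protein level" under 100 mg/24h, again with an FLC substitute.
- **SD (f):** the remainder, "Not meeting criteria for CR, VGPR, PR, MR or progressive disease".

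Section 6.2.7 states: "Clinical benefit rate (CBR) is sCR+CR+VGPR+PR+MR". SD is therefore excluded. The CBR is a named secondary objective in 3.2: "Clinical benefit rate (minor response [MR] or better) after 8 cycles of treatment per modified IMWG criteria for MM".

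Nothing in 6.2 says that a patient who exceeds one MR band but misses PR still counts as MR.

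**The concern.** Response categories should be ordered: a larger fall in either compartment should never give a worse category. Two capped bands joined by *and*, with SD as the residual, break that order. A patient can do better than an MR patient on serum, on urine, or on both, and still be scored SD.

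At stake is the CBR after 8 and 24 cycles. It would omit some patients whose response exceeds that of patients it counts, and assessors would have to depart from the text to avoid this. The MR threshold also appears in the continuation and restart text of 1.0 and 2.1, where for patients with at least MR "after 8 cycles, treatment can be continued for an additional 16 cycles to a maximum of 24 cycles". The same definition is thus read in two places.

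**Working it through.** **Inputs.** The rules in 6.2.2(c)-(f), the CBR definition in 6.2.7 and the total of 16 patients in section 9. Baseline urine values are assumptions, shown as a range, because the documents give no distribution. The check covers the M-protein limbs only, with no progression and no plasmacytoma.

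**Notation.** s and u are the percentage falls in serum and urine M-protein, U0 is baseline urine M-protein (mg/24h), and R = U0 × (1 − u/100) is what remains.

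- VGPR (reduction limb): s ≥ 90 and R < 100
- PR: s ≥ 50 and (u ≥ 90 or R < 200)
- MR: 25 ≤ s ≤ 49 and 50 ≤ u ≤ 89
- SD: otherwise

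**Literal scoring.**

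| Serum fall | Urine, mg/24h (fall) | Category |
|---|---|---|
| 30% | 1500 to 300 (80%) | MR |
| 60% | 1500 to 300 (80%) | SD: urine misses PR, serum is above the MR cap |
| 40% | 1500 to 75 (95%) | SD: serum misses PR, urine is above the MR cap |
| 95% | 2000 to 300 (85%) | SD |
| 60% | 600 to 180 (70%) | PR, because R < 200 |
| 60% | 1000 to 150 (85%) | PR, because R < 200 |

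The second patient equals the first on urine and is better on serum. The third is better on both. Both score worse.

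**Urine above its band, serum 25-49%.** PR fails on serum and MR fails on the urine cap, so the result is SD at every baseline urine level.

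**Serum at 50% or more, urine in band.** PR is missed only if R ≥ 200. A fall of at least 50% leaves R ≤ U0/2, so R ≥ 200 requires U0 ≥ 400. Over the 40 whole-percent urine falls from 50 to 89, SD results when u ≤ 100 × (1 − 200/U0):

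| U0 | SD when u is | Share of grid |
|---|---|---|
| 300 | never | 0/40 = 0% |
| 400 | 50 | 1/40 = 2.5% |
| 500 | 50-60 | 11/40 = 27.5% |
| 800 | 50-75 | 26/40 = 65% |
| 1000 | 50-80 | 31/40 = 77.5% |
| 1500 | 50-86 | 37/40 = 92.5% |
| 2000 | 50-89 | 40/40 = 100% |

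These are shares of an even grid, not expected patient frequencies. Section 5.1 lists urine M-protein of 500 mg/24h or more among its entry routes, so the relevant baselines can occur.

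**Size.** One patient is 1/16 = 6.25 points. With assumed counts and exact 95% intervals: 4/16 = 25.0% (7.3-52.4), 5/16 = 31.3% (11.0-58.7), 6/16 = 37.5% (15.2-64.6).

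**Primary design.** Section 9's figures reproduce. The early-stopping probability is 0.95^12 = 0.540 at a 5% response rate and 0.75^12 = 0.032 at 25%. Expected sizes are 12 + 4 × (1 − 0.540) = 13.84 and 12 + 4 × (1 − 0.032) = 15.87. None of this uses MR, since ORR starts at PR (6.2.6).

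**Does a floor restore order?** With s ≥ 25 and u ≥ 50 as lower bounds, in a patient not meeting PR or better, raising s or u from any MR point leaves the patient at MR or higher.

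**The case against.** The strongest reply is that the problem is narrower than it looks, and much of that reply stands.

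- **Not every patient above a band is lost.** A reader might infer that exceeding either band always leads to SD. It does not: a serum fall of 50% or more with urine in band is PR whenever residual urine is below 200 mg/24h, and below a 400 mg/24h baseline the serum direction never produces the error.
- **Serum-only patients.** A reader might infer that anyone without urine M-protein can never be MR, so that in them the CBR collapses to the ORR. The text does not establish this. The PR clause is also worded as a urine reduction, so a strict reading that bars MR would arguably bar PR too. Section 6.2.1(c), although about confirmation, treats urine as relevant when it is the primary determinant of response. This is an ambiguity to resolve.
- **The 49-50% and 89-90% gaps** may be no more than whole-percent rounding.
- **Frequency is unknown.** High urine M-protein is one of several entry routes in 5.1, and none of the risk factors in 5.1.1 is urine protein. The 6.25 points is the weight of any one patient among 16; it is not an estimate of bias.
- **Limited consequence.** The CBR carries no test or decision rule, and section 9 does not name it.

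None of this removes the ordering failure in mixed responses. Appeal to a standard source would not remove it either: 6.2.2 describes its criteria as modified, and this is the text that assessors will apply.

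**Conclusion.** The point holds in a limited form. As written, 6.2.2(e) scores as SD a patient who exceeds one MR band without meeting PR, while a smaller response is MR. It occurs without exception when serum falls 25-49% and urine falls 90% or more. With serum down 50% or more and urine in band, it occurs only when urine stays at or above 200 mg/24h. Read literally, MR also gives no route for patients without urine M-protein, without serum M-protein, or with FLC-only disease. 6.2.1(b) says that FLC-only patients are to be evaluated by FLC criteria, but 6.2.2 provides these for VGPR and PR and not for MR.

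The size is 6.25 points of CBR per affected patient if all 16 are enrolled and analysed. The number affected cannot be derived, so a statement that the CBR understates activity by some amount is not supported. Nor is any effect on the primary conclusion: ORR, the Simon rule, its error rates and N do not depend on MR. The effect on continuation after cycle 8 is also uncertain, because 2.1 separately refers to continued clinical benefit.

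**What to change.** For scoring the CBR, define MR by lower bounds only, in a patient who does not meet PR or better and has no progressive disease:

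- serum M-protein reduced by at least 25%, if serum M-protein is measurable at baseline; and
- 24-hour urine M-protein reduced by at least 50%, if urine M-protein is measurable at baseline.

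Remove the upper limits of 49% and 89%, and the 49% limit in the plasmacytoma clause. State how FLC-only patients are scored for MR, as is already done for PR and VGPR.

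The cost is small: a short rewrite of 6.2.2(e), with no new visits or data and no change to ORR or the Simon design. The CBR can only rise or stay the same, and it departs slightly from the banded wording; the report should say so.

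Because the MR threshold also appears in the continuation and restart text of 1.0 and 2.1, the sponsor must reconcile those sections with 6.2.2. No continuation rule is proposed here.
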